### 13.4 Collection, Management and Reporting Procedures

The period of collection of adverse events starts from the time of signature of the Informed Consent Form (ICF) by the subject until the end of the subject's participation in the clinical study.

If a Serious Adverse Event (SAE) is on-going at the final clinical trial visit, it should be followed by the Investigator until it has resolved or has reached a stable condition.

After the subject completes the clinical study, the Investigator should also inform the Sponsor (see Sponsor's contact details below) if he/she becomes aware of an SAE involving a subject who has participated in the clinical study.

At each post-enrollment visit, the Investigator will question the subject about AEs using an open non-persuasive question to elicit reporting of AEs, for example "*Have you noticed any change in your child's health since the last visit?*" Direct questioning and examination will be performed when appropriate.

The Investigator will obtain and maintain in the subject's files all pertinent medical records, and (if applicable) information and medical judgment from colleagues who assisted in the treatment and follow-up of the subject. If necessary, the Investigator will contact the subject's personal physician or hospital staff to obtain further details.

#### 13.4.1. Management and reporting procedures for undesirable effects (i.e., related adverse events)

Undesirable effects should be recorded in the CRF in a summary table with at minimum the subject number, AE number, AE diagnosis or signs and symptoms, location, date of onset, seriousness, severity, action taken, relationship, date of resolution and concomitant treatment associated as well as a detailed narrative of the event.

In addition, based on his/her medical judgment, the Investigator will assess whether an undesirable effect requires immediate (i.e., within 24 hours) reporting to the Sponsor. In such cases, the summary table will be sent to the Sponsor, along with the AE narrative and any other relevant information (concomitant treatments, product weighing, ...).

Protocol Version: 01

This document contains confidential, proprietary information.

Protocol GLI.04.US.SL.023

CONFIDENTIAL

All undesirable effects should be appropriately documented, i.e., any relevant information such as demographics, medical history and concomitant therapies should be recorded in the CRF.

The Investigator is to monitor and record the progress of the adverse effect until the last subject's study visit.

The Investigator is to update the AE narrative as appropriate; each time follow-up information is collected and when the final outcome of the adverse effect is known.

#### 13.4.2. Management and reporting procedures for Serious Adverse Events

The Investigator is to take the following steps:

1. Take prompt and appropriate medical action, if necessary. The safety of clinical trial subjects is the first priority
2. Ensure the AE is classified as an SAE. Immediately inform the Sponsor's representative of the event by email (see both contact details below) and discuss further actions to be taken:

Global Vigilance email: [[contact]](mailto:[contact])

US Vigilance email: [[contact]](mailto:[contact])

3. Complete the Serious Adverse Event (SAE) form provided by the Sponsor's representative **Within 24 hours**, send by e-mail **to the Sponsor's representative** the completed SAE form, accompanied any other relevant information (e.g., test results or medical records).
4. Monitor, record and send to Sponsor's representative the progress of the event until it resolves or reaches a stable outcome, with or without sequelae (send the updated SAE form with follow-up information and any other relevant information to Sponsor's representative).
5. Obtain and maintain in the subject's file all pertinent medical records, information, and medical judgments from colleagues who assisted in the treatment and follow-up of the subject. If necessary, contact the subject's personal physician or hospital staff to obtain further details.
6. If applicable, comply with the regulatory requirement(s) related to the reporting of SAEs to the Institutional Review Board (IRB) / Independent Ethics Committee (IEC).

#### 13.4.3. Anticipated Adverse Events for Sculptra

Information regarding anticipated AEs for *Sculptra* is included in the commercial IFU.

Protocol GLI.04.US.SL.023

CONFIDENTIAL

**14. ETHICAL AND REGULATORY PROCEDURES****14.1 Research Standards/Good Clinical Practice**

This study will be conducted in accordance with all applicable guidelines for the protection of human subjects for research as outlined in 21 CFR 50 the accepted standards for Good Clinical Practice (GCP), and the standard practices of SGS Stephens in accordance with the protocol and amendment(s) as applicable.

**14.2 Quality Assurance/Audit/Inspection**

To ensure compliance with GCP and all applicable regulatory requirements, Galderma Laboratories, L.P. may conduct a quality assurance audit of the site records, and the regulatory agencies may conduct a regulatory inspection at any time during or after completion of the study. The Investigator must agree to grant the auditor(s) and inspector(s) direct access to all relevant documents and to allocate their time and the time of their staff to discuss any findings/relevant issues.

**14.3 Institutional Review Board**

This study (protocol, ICF and all addenda) will be reviewed and approved by Sterling IRB. The study will not be activated and subjects will not be consented, receive any study products, or participate in any study procedures until the IRB has approved the protocol and the ICF. In addition, the IRB will review the study before any significant change in the protocol is initiated. After each review, the IRB's approval will be documented in a letter to the Investigator and a copy of the IRB approval letter will be forwarded to the Sponsor.

**15. STUDY CONDUCT CONSIDERATIONS****15.1 Clinical Monitoring**

The conduct of the study will be closely monitored by representatives of Galderma Laboratories, L.P. following GCP, ICH guidelines, applicable SOPs, guidelines, and all local regulations. The clinical investigation will be monitored to ensure that: the rights and well-being of the subjects are protected; the reported data are accurate, complete and verifiable from applicable source documents; and the study is conducted in accordance with the currently approved protocol and any other study agreements, GCP, and all applicable regulatory requirements. The Investigator will allow the Galderma Laboratories, L.P. representatives to have access to all study records, CRF/eCRF, corresponding subject medical records, and any other documents considered source documentation. The Investigator also agrees to assist the representatives, if required, which can include AE reporting.

**15.2 Study Deliverables**

All study data and digital images will be forwarded to the Sponsor. Images will be labeled with study number, subject number, and timepoint.

Protocol Version: 01

This document contains confidential, proprietary information.

Protocol GLI.04.US.SL.023

CONFIDENTIAL

**15.3 Data Collection**

Investigators must keep accurate records of all subjects' visits and all procedures done, being sure to include all pertinent study related information from which CRF/eCRF data will be recorded. Data for this study may be recorded in the subject's chart (e.g., source documents / electronic records) or if approved by the Galderma Laboratories, L.P. directly into CRF/eCRFs. If electronic records are maintained, the method of verification must be determined in advance of starting the study. The process of administering the informed consent must also be documented. Any and all side effects and AEs with the concomitant therapies associated must be thoroughly documented. Results of any diagnostic tests conducted during the study should be included in the source documentation. Pertinent telephone conversations with the subjects and/or Galderma Laboratories, L.P. concerning the study will be documented and kept on file.

It is required that the author of an entry in the source documents be identifiable. Direct access to all source documentation (medical records) must be allowed for the purpose of verifying that the data recorded in the CRF/eCRF are consistent with the original source.

Only designated individuals may complete the CRF/eCRFs. The principal Investigator will review the reported data and certify that the CRF/eCRFs are accurate and complete.

After monitoring has occurred at the clinical site(s) and the CRF/eCRFs have been reviewed, additional data clarifications and/or additions may be needed including AE reporting. Data clarifications and/or additions are documented and are part of each subject's CRF/eCRFs.

**15.4 Data Management**

A double-entry method will be used to enter data captured on paper records into a spreadsheet database to ensure accurate data transfer, and any missing data and/or inconsistencies will be identified and corrected.

The self-assessment questionnaire will be completed by subjects electronically using HIPAA-compliant SurveyMonkey online survey software. Paper questionnaires may be completed if needed.

All images taken from the study will be saved and shared to the Sponsor via a data-protected platform.

**15.5 Record Retention**

The Investigator is required to maintain up-to-date, complete regulatory documentation as indicated by Galderma Laboratories, L.P. and the Investigator's files will be reviewed as part of the ongoing study monitoring. The records must be easily accessible when needed (e.g., for a Galderma Laboratories L.P.'s audit or regulatory inspection) and must be available for review in conjunction with assessment of the facility, supporting systems, and relevant site personnel. Financial information is not subject to regulatory inspection and should be kept separately.

Galderma Laboratories, L.P. will inform the Investigator of the time period for retaining the site records in order to comply with all applicable regulatory requirements. The minimum retention time will meet the strictest standard applicable to a particular site, as dictated by local laws/regulations, Galderma Laboratories, L.P. SOPs, and/or institutional requirements.

Protocol Version: 01

This document contains confidential, proprietary information.

Protocol GLI.04.US.SL.023

CONFIDENTIAL

The Investigator should take measures to prevent accidental or premature destruction of these documents. If the Investigator retires, relocates, or for other reasons withdraws from the responsibility of keeping the study records, custody must be transferred to a person who will accept the responsibility. Galderma Laboratories, L.P. must be notified in writing of the name and address of the new custodian.

### **15.6 Changes in Study Conduct/Amendments**

No amendment will be done for modification(s) due to change in logistical or administrative aspect of the study (e.g., change in monitors, change of telephone numbers). In such a case, the appropriate institution(s) and/or person(s) will be notified of the changes.

Modification of the protocol is prohibited without prior written agreement in the form of a protocol amendment. All amendments will be created by Galderma Laboratories, L.P. and must be approved by the IRB prior to implementation except when required to mitigate immediate safety risks or when the changes involve only logistical or administrative revisions.

Amendments may necessitate that the informed consent and other study-related material be revised. If the consent form is revised, all Subjects/subjects currently enrolled in the study may be required by the IRB to sign the approved, revised informed consent form.

## APPENDIX I: INGREDIENT LISTS

### HEALING OINTMENT

#### Active ingredient:

Petrolatum 71.5%

#### Inactive ingredients:

Cetearyl Ethylhexanoate

Butyrospermum Parkii (Shea) Butter

Beeswax

Microcrystalline Wax

Tocopheryl Acetate (Vitamin E Acetate)

Protocol GLI.04.US.SL.023

CONFIDENTIAL

**APPENDIX II: SELF-ASSESSMENT QUESTIONNAIRE****Day 1**

	Strongly agree 5	Agree 4	Neither agree nor disagree 3	Disagree 2	Strongly disagree 1
The product instantly soothes my baby's irritated skin					
I've noticed an instant relief on baby's irritated skin after applying the product					
My baby's skin feels smooth					
My baby's skin feels soft					

**Visit 2 (Day 7 or Week 1)**

	Strongly agree 5	Agree 4	Neither agree nor disagree 3	Disagree 2	Strongly disagree 1
The product does not feel greasy upon application					
My baby's skin feels softer and smoother					
The product soothes my baby's skin					
The product is easy to wipe/wash off without leaving any greasy residue					
The product lasts between diaper changes					
The product does not leave the skin feeling greasy					
This product is gentle on my baby's delicate skin					
This product has started to repair my baby's irritated skin					
This product provides a protective layer for my baby's skin					
I've noticed an immediate relief on my baby's skin after the product application					

**Visit 3 (Day 21 or Week 3)**

	Strongly agree	Agree 4	Neither agree nor disagree	Disagree 2	Strongly disagree 1
--	-------------------	------------	----------------------------------	---------------	---------------------------

Protocol Version: 01

This document contains confidential, proprietary information.

Protocol GLI.04.US.SL.023

CONFIDENTIAL

	5		3		
The product continuously protects my baby's skin from diaper rash					
The product provides long-lasting diaper rash relief					
Diaper rash flares are less frequent since starting this product					
Diaper rash flares are less intense since starting this product					
I have enjoyed using this product on my baby					
My baby's skin quality has improved since starting this product					
I love how this product leaves my baby's skin feeling soft and soothed					
My baby is less fussy since starting this product					
I worry less about my baby's diaper rash since starting this product					
My baby sleeps better since starting this product					

	Yes	No
I would continue using this product on my baby		
I would purchase this product		
I would recommend this product to other parents		
I would switch from my current baby ointment to this product		

**Testimonials** (please provide any comments on your experience, treatments, satisfaction/dissatisfaction, or anything related to this study)

---

---

---

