### 6.3 Inclusion Criteria

1. Subjects of 2-~~24~~35 months of age
2. Females and/or males
3. Subjects of any race and ethnicities
4. Subjects diagnosed with mild-to-moderate diaper rash
5. Subjects of any Fitzpatrick skin types I-VI
6. Subjects with healthy immune systems
7. Willing to be photographed at each visit (optional)
8. Willing to abstain from use of any other topical diaper rash treatments (ointments, moisturizers, emollients, creams, and wipes) other than the assigned test product and skincare products that have been routinely used on the diaper area during the duration of the study
9. Willing to continue using regular brands of face/body cleanser and not to begin use of any new skincare products other than the test product for the duration of the study
10. Parent/legal guardian/legal guardians must be at least 18 years old and are willing and able to present proof of legal guardianship
11. Parent/legal guardian/legal guardian with ability to read, understand and give consent for participation in the study
12. Parent/legal guardians/legal guardians willing to sign a photography release form
13. Parent/legal guardian/guardian must agree to adhere to the procedures and requirements of the study and to report to the site on the day(s) and at the time(s) scheduled for the assessments

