### 6.4 Exclusion Criteria

1. Subject diagnosed with severe diaper rash
2. History of allergy or hypersensitivity to any ingredient of the test product
3. Presence of any disease or lesions near or on the area to be treated, e.g.,
  - a. Inflammation, active, or chronic infection in or near the treatment area
  - b. Psoriasis, eczema, rosacea, atopic dermatitis, herpes zoster/herpes simplex, and acanthosis
  - c. Scars or deformities

Protocol GLI.04.US.SL.023

CONFIDENTIAL

4. History of coexisting bacterial infections or medical conditions with uncontrolled gastrointestinal diseases and/or bowel movements
5. History of severe elastosis and/or excessive sun exposure that, in the opinion of the Investigator, could have affected the outcome of the study
6. Planning on having surgeries and/or invasive medical procedures during the course of the study
7. Treatment with chemotherapy, immunosuppressive agents, inhaled corticosteroids, immunomodulatory therapy (e.g., monoclonal antibodies or antiviral treatment for human immunodeficiency virus or hepatitis C)
8. Current use of topical corticosteroids, topical prescription, or oral antibiotics in the treatment area, or use within last 2 weeks
9. Current use of over-the counter topical medications for diaper rash
10. History of cancer or previous radiation near or on the treatment area
11. Human immunodeficiency virus positive or active hepatitis
12. Presence of dermal markings on or near the treatment area that, in the opinion of the Investigator, will interfere with the clinical assessments
13. Any medical condition that, in the opinion of the Investigator, would make the subject unsuitable for inclusion (e.g., a chronic or relapsing disease that may interfere with the outcome of the study)
14. Other condition preventing the subject from entering the study in the Investigator's opinion, (e.g., subjects failing baseline assessments, subjects not likely to avoid other cosmetic treatments in the treatment area, subjects anticipated to be unavailable or incapable of understanding the study assessments or having unrealistic expectations of the treatment result).
15. Study site personnel, close relatives of the study site personnel (e.g., parent/legal guardians, children, siblings, or spouse), or employees and close relatives of employees at the Sponsor company.
16. Participation in any interventional clinical study within 30 days of screening

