### 8.3.3. General Study Instructions

- Throughout the study, parents/legal guardians must ensure subjects to avoid extended periods of sun exposure. Extra care should be taken to wear sunscreen and accessories (i.e., hat) and avoid sun exposure from 10 am to 3 pm.
- Do not use any topical diaper rash and/or moisturizing products on the test area (such as sunscreen, lotion, cream, oil, ointment, wipes), other than the assigned study product, for the duration of the study.
- Do not start using any new body care products other than the provided study product.
- Parents/legal guardians must use the same type of diapers for the duration of the study.

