**Table 1. Study Visits and Assessments**

Procedure	Visit 1	Visit 2	Visit 3
	Day 0	Week 1 or Day 7	Week 3 or Day 21
	Screening/Baseline	Follow-up	Follow-up
Informed consent	X		
Demographic	X		
Inclusion and exclusion criteria	X		
Concomitant medications	X	X	X
Digital photography	X	X	X
Safety assessment	X	X	X
Efficacy assessment	X	X	X
Self-assessment questionnaire	X*	X	X
Adverse events		X	X
Study product	W/D	I/W/D	I/C/W
Subject diary	D	C/R/D	C/R

\*At home questionnaire after first application.

For products and daily diaries: D=Distribute, C=Collect, R=Review, W=Weigh, and I=Inspect (visually)

Protocol Version: 01

This document contains confidential, proprietary information.

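### The Visit 3 switch item presumes a current baby ointment, gives no way to say there is none, and is analysed without a defined denominator

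*Combined protocol and SAP*

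**What the plan says.** **The item.** Appendix II, Visit 3, ends with four Yes/No statements, the last being "I would switch from my current baby ointment to this product". It has no third answer.

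**Text suggesting that a parent may have no such ointment.** Exclusion 8 in Section 6.4 covers "Current use of topical corticosteroids, topical prescription, or oral antibiotics in the treatment area, or use within last 2 weeks", and exclusion 9 covers "Current use of over-the counter topical medications for diaper rash". During the study, Section 8.3.3 instructs "Do not use any topical diaper rash and/or moisturizing products on the test area", and names ointments among the products meant.

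**Text suggesting that some parents do have one.** Inclusion 8 in Section 6.3 exempts from abstention "skincare products that have been routinely used on the diaper area during the duration of the study". Section 8.3.2 tells parents to give up diaper-rash treatments and use the study product in their place, which presupposes that some were using them. Section 6.5 requires treatments and therapies from the 30 days before enrolment to be recorded.

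**The analysis.** Section 12.4 reports the frequency and percentage of every response option for each question. For items with no baseline response it adds a binomial (sign) test of favorable against unfavorable answers. It reads a higher favorable percentage with a significant p value as positive perception. It sets no rule for parents to whom an item does not apply.

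**The flare items.** The same form asks for agreement, on five points with a neutral middle, that "Diaper rash flares are less frequent since starting this product" and "Diaper rash flares are less intense since starting this product". Table 1 schedules no pre-study flare assessment, and its footnote describes the first questionnaire as "At home questionnaire after first application".

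**The concern.** A preference for switching has meaning only for a parent who has something to switch from. If the respondents are a mixture, the Yes percentage blends a real product comparison with answers that can mean only general goodwill or general indifference, and the form gives no means of separating them.

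The item feeds the secondary satisfaction objective and the Section 4.2 hypothesis of a statistically significant share of favorable responses. It is also the one item that sets the study product against another product, so a reader of the results may well take it as a product comparison.

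A related and weaker point applies to the flare items. They ask for a before-and-after judgement, but no earlier flare frequency or intensity is scheduled for collection, and every infant enters with a rash present. A high agreement rate would say how parents feel. It would not show that flares became rarer or milder.

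**Working it through.** The plan states no expected percentage, power or effect size for the questionnaire, so there is no figure of its own to reproduce. The check asks how far inapplicable answers could move the switch result.

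**Inputs from the documents**
- At most 30 completers (Section 6.1).
- Two-sided tests at 5% (Section 12.1).
- Sign test of favorable against unfavorable, so the null proportion is 0.5 (Section 12.4). Yes is taken as favorable.

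**Input that is an assumption:** k, the number of parents without a prior ointment. The documents do not give it.

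**Step 1: the threshold with all 30 answering.**
Two-sided p for r Yes = 2 × Σ C(30, j) / 2^30, summed over j = r to 30.
- r = 21: 2 × 22,964,087 / 1,073,741,824 = 0.043
- r = 20: 2 × 53,009,102 / 1,073,741,824 = 0.099

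So 21/30 (70%, exact 95% interval 51% to 85%) is the smallest significant Yes count.

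**Step 2: illustration with k = 12.** Suppose 18 parents had an ointment and split evenly, 9 Yes and 9 No.
- All 12 others tick Yes: 9 + 12 = 21, 21/30 = 70%, p = 0.043.
- Eleven of the 12 tick Yes: 9 + 11 = 20, p = 0.099.
- The 12 split evenly: 9 + 6 = 15, 15/30 = 50%.
- All 12 tick No: 9/30 = 30%, p = 0.043 in the other direction.

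The parents for whom the question has meaning show no preference in any of these cases. The reported figure runs from 30% to 70%.

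**Step 3: range over k.** If all k inapplicable answers are Yes, prior users need only 21 − k of 30 − k:

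| k | Yes needed among prior users |
|---|---|
| 0 | 21/30 (70%) |
| 5 | 16/25 (64%) |
| 10 | 11/20 (55%) |
| 15 | 6/15 (40%) |
| 20 | 1/10 (10%) |

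If all k are No, the largest possible Yes count is 30 − k. Once k reaches 10 this is at most 20, so a significant Yes result cannot occur even if every prior user would switch.

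**Step 4: what restricting the denominator costs.** The smallest significant count is 15/20 (p = 0.041), 12/15 (p = 0.035), 9/10 (p = 0.021) or 6/6 (p = 0.031). With 5 respondents, 5/5 gives 2 × 1/32 = 0.0625, so significance is out of reach. If 80% of prior users would truly switch, the chance of a significant result is 94% with 30 respondents, 80% with 20, 65% with 15 and 38% with 10.

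**The case against.** **Some parents will have a usual ointment.** A reader might infer from exclusions 8 and 9 that no enrolled family can have a current ointment, which would make the item empty. The documents do not support that. The exclusions concern medications and prescription products and do not plainly cover an ordinary emollient. Inclusion 8 and Section 8.3.2 both point to existing users, and the phrase can be read as the family's usual product, paused for the study. This objection stands, and it is why the point concerns a mixed sample.

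**Nothing makes the item mandatory.** A parent could leave it blank, particularly on the paper form that Section 15.4 allows. Section 12.4 also limits the sign test to applicable questions with designated favorable answers. This is fair, but the plan lists neither the applicable questions nor the designations, and says nothing on inapplicable answers. A blank would not show why it was left.

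**Prior therapies are recorded.** This is correct for the 30 days in Section 6.5. What is missing is any link from that record to this item, and it is unclear whether a non-drug baby ointment counts there as a treatment.

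**The flare items are opinions.** Section 10.3 presents the questionnaire as perception and satisfaction, Section 12.4 interprets it that way, and the flare items offer a neutral answer. A reader might infer that the plan claims a reduced flare rate, or that it must measure flares beforehand. Neither follows from the documents. Nor are the switch and flare items the only comparative ones: Visit 3 also asks about skin quality, fussiness, worry and sleep since starting.

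**The illustration is built from extremes.** This is true. Steps 2 and 3 show what the plan permits. They do not predict what will happen.

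**Conclusion.** The point holds as a minor one. The switch item lacks a not-applicable answer and a defined denominator, and the eligibility and instruction texts (exclusions 8 and 9, inclusion 8, Sections 8.3.2 and 8.3.3) disagree on whether a current product can exist. With an evenly split group of 18 prior users, the reported Yes percentage could lie anywhere from 30% to 70%, and is nominally significant at either end. That range rests on an assumed 18/12 split. In that example significance also needs all 12 inapplicable answers to fall the same way, since 11 of 12 is not enough.

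The flare items and the other since-starting items can be reported as what parents perceived. They cannot serve as evidence that flares became less frequent or less intense.

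The effect is confined to one of 28 questionnaire items (4 on Day 1, 10 at Visit 2, 14 at Visit 3), plus the interpretation of the since-starting items. The primary skin-grading analysis and the safety assessments are untouched.

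**What to change.** 1. Reword the switch item to refer to *the ointment used before the study*, and add the answer *not applicable / no previous ointment*.
2. Ask parents directly whether they used an ointment on the diaper area before the study, because the Section 6.5 record may miss a non-drug product.
3. State in Section 12.4 that the switch item is tabulated and tested only among parents who report a prior product, and show the not-applicable count beside it.
4. State that the flare items and the other since-starting items are reported as parental perception, and are not evidence of a reduced flare rate.
5. Reconcile inclusion 8, exclusions 8 and 9, and Sections 8.3.2 and 8.3.3 on which products a family may have been using and may keep using.

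The cost is a few edits to an electronic survey, one added question and two sentences in the analysis section. The drawback is a smaller denominator for the switch item and hence less power, as Step 4 shows. With few prior users the percentage and its interval are better given without a test.
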